## I. Objective and Specific Aims

Our objective is to perform a prospective, randomized, interventional trial of Emergency Department (ED) administration of DSUVIA versus standard care pain management comparing pain treatment outcomes in injured patients with moderate to severe pain.

**AIM #1:** To determine if, among injured patients with moderate to severe pain, treatment with DSUVIA compared to standard care pain treatment in the ED reduces the Verbally administered Numeric Rating Scale (VNRS) for clinical pain measurement (0-100) at 30 minutes.

Hypothesis #1: Null Hypothesis: There will be no difference in the pain score at 30 minutes of patients who received DSUVIA as compared to standard care pain medicine in trauma patients

**AIM #2**: To determine if, among injured patients with moderate to severe pain, treatment with DSUVIA compared to standard care pain treatment in the ED reduces adverse effects and events related to pain medication(s) including nausea/vomiting, headache, dizziness, hypoxia, hypotension, and need for advanced airway.

Hypothesis #2: Null Hypothesis: There will be no difference in the rate of adverse events of nausea/vomiting, headache, dizziness, hypoxia, hypotension and need for advanced airway in patients who received DSUVIA as compared to standard care pain medicine in trauma patients.

**AIM #3:** To determine if, among injured patients with moderate to severe pain, treatment with DSUVIA compared to standard care pain treatment in the ED improves pain treatment effectiveness including serial VNRS scores (every 30 minutes), the need for rescue narcotic administration, the time needed to reduce the VNRS pain score by 10 points, time-weighted summed pain intensity difference, patient global assessment (PGA), Six Item Screener (SIS) cognitive assessment and Richmond Agitation-Sedation Scale scores.

Hypothesis #3: Null Hypothesis: There will be no difference in the pain treatment effectiveness, need for rescue narcotic administration, time to reduction of 10 points of VNRS pain score by 10 points, the time-weighted summed pain intensity difference, patient global assessment, Six-Item Screener and the Richmond Agitation-Sedation Scale scores in patients who received DSUVIA as compared to standard care pain medicine in trauma patients.

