The NAEMSP guidelines focus on intravenous (IV) fentanyl and morphine because of wide availability among American EMS services. Use of IV opioids is limited by the need to obtain IV access, which can be time consuming, is associated with a significant failure rate, and may lead to increased exposure in a tactical environment. The US military uses oral transmucosal fentanyl citrate (OTFC) which can be administered without IV access, but has slow absorption. Furthermore, safety data on OTFC, outside of long-term analgesia for cancer patients, is not well described. Given these significant limitations, an alternative to IV opioid analgesics in necessary. The ideal agent has robust stability, easy delivery, rapid onset, minimizes altered mental status and has a wide therapeutic index. In addition, the ideal agent would have a longer duration of action and an improved side effect profile as compared to the current standard care.

Sufentanil is a potent opioid analgesic derived from fentanyl with no active metabolites, rapid onset, and a therapeutic index superior to morphine and fentanyl. Sufentanil is highly lipophilic and rapidly achieves equilibrium in the brain; the time to analgesia is similar to IV morphine. When administered sublingually, sufentanil is 53% of the IV bioavailability within one minute and provides analgesia within 15 minutes. Sufentanil has a low incidence of side effects, with nausea, headache, dizziness, and vomiting being the most common. As with any opioid, respiratory depression and hypoxia can occur but was observed to be <1%. Similar studies found no clinically significant changes in vital signs after the administration of sublingual sufentanil in post-operative patients. Sufentanil was effective in a cohort of patients with painful injuries presenting to the ED with pain reduction seen in less than 15 minutes and persisting for 2 hours.

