## IV. Outcomes

**Primary Outcome:** The primary outcome for the pilot trial will be the Verbally administered Numeric Rating Scale (VNRS) for clinical pain measurement (0-100) at 30 minutes following randomized medication administration. 

Secondary Outcomes: Secondary outcomes will include adverse events including hypoxia needing supplemental oxygen (SpO2 < 90%); hypotension (systolic blood pressure < 90mmHg); advanced airway or bag mask ventilation; incidence of nausea/vomiting/headache/dizziness requiring treatment; serial (30 minute intervals until ED discharge, up to 120 minutes or rescue narcotic administration) measurements of a) VNRS for clinical pain (0-100), b) Patient Global Assessment (PGA) of Pain Control, c) Richmond Agitation-Sedation Scale (RASS) scores, and d) time-weighted Summed Pain Intensity Difference (SPID); number of rescue narcotic doses at 30 minutes and during ED stay (up to 120 minutes); time to a reduction in VNRS pain score of 10 points; patient cognitive function as assessed by the Six Item Screener (SIS) at 30 minutes; Healthcare Professional Global Assessment (HPGA) of the method of pain control at 30 minutes; and acceptability of pain treatment to health care providers.

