#### Secondary Outcome Definitions:

**Hypoxia, hypotension or need for advanced airway:** The principal safety outcome for the trial will be the incidence of serious adverse events following the first dose of analgesic following randomization including hypoxia (SpO2 < 90%), hypotension (SBP < 90 mmHg) or the need for advanced airway management (placement of an endotracheal tube, supraglottic airway or bag mask ventilation) until ED discharge (up to 120 minutes), when feasible.

Composite outcome of nausea, vomiting, headache, and/or dizziness requiring treatment: The incidence of nausea, vomiting, headache, and/or dizziness requiring treatment will be recorded for initial 30 minutes, when feasible.

Verbally administered Numeric Rating Scale (VNRS) pain measurements (0-100) at 30- minute intervals: VNRS for clinical pain (0-100) measurements at approximate 30-minute intervals until discharge from the ED (up to 120 minutes) or rescue narcotic administration, will be obtained when feasible.

**Patient Global Assessment (PGA) of Pain Control at 30-minute intervals:** The PGA of the method of pain control at approximate 30-minute intervals until discharge from the ED (up to 120 minutes) or rescue narcotic administration, will be obtained when feasible. The research team will read the following statement aloud to the subject and the response will be recorded: "Overall, would you rate this method of pain control during the last 30 minutes/hours as being poor (1), fair (2), good (3), or excellent (4)?"

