## VI. Statistical Analysis Plan

Random Assignment: Participants will be randomly assigned in a 1:1 ratio to either DSUVIA or standard of care, stratified by site. Within each stratum, random assignment will be blocked, with random block size of two and four.

Analyses: All analyses will be carried out based on the intention-to-treat principle. Of those randomly assigned, the analyses will begin by describing the overall characteristics of the study population at the time of random assignment. Baseline characteristics will be described overall using summary statistics (e.g., means, standard deviation, percentages) and graphical techniques (e.g., histograms, box plots). Baseline characteristics between the two groups will be compared using t-tests or Wilcoxon tests for continuous variables and a chi-square tests for discrete variables.

The analyses for each aim are presented below.

AIM #1: To determine if, among injured patients with moderate to severe pain, treatment with DSUVIA compared to standard care pain treatment in the ED reduces the Verbally Administered Numeric Rating Scale (VNRS) for clinical pain measurement (0-100) at 30 minutes.

A t-test will be used to compare the mean VNRS scores between the two treatment groups. A multivariable regression model will be used to compare the means after adjusting for stratification

variables (i.e., site) and baseline characteristics not balanced through random assignment. All assumptions of the analyses will be tested (e.g., normality of residuals). If any assumptions are violated, transformations of the data will be investigated and the transformed data will be analyzed and evaluated. If an adequate transformation cannot be identified, nonparametric methods will be used.

AIM #2: To determine if, among injured patients with moderate to severe pain, treatment with DSUVIA compared to standard care pain treatment in the ED reduces adverse effects and events related to pain medication(s) including nausea/vomiting, headache, dizziness, hypoxia, hypotension, and need for advanced airway.

The adverse events will be analyzed in composite (any of them) and individually. For each, a chi-square test will be to compare the proportion of events between the two treatment groups. A multivariable logistic regression model will be used to compare the proportions after adjusting for stratification variables (i.e., site) and baseline characteristics not balanced through random assignment

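### Ordinary logistic regression for each Aim 2 event has no finite treatment estimate when one arm has no events, which is likely for components near 1%; a lesser point is that the pooled composite covers two risk periods

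*Combined protocol and SAP*

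**What the plan says.** **Analysis.** In Section VI, Aim #2, the plan states: "The adverse events will be analyzed in composite (any of them) and individually". Each is compared between arms by a chi-square test. For the adjusted comparison, a multivariable "logistic regression model will be used to compare the proportions after adjusting for stratification variables (i.e., site"), and for baseline factors that turn out unbalanced. Aim #1 has a fallback to transformation or nonparametric methods if assumptions fail. Aim #2 has no fallback for few or no events.

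**Expected rates.** Section II says of opioids, in its description of sufentanil, that "respiratory depression and hypoxia can occur but was observed to be <1" per cent. It describes sufentanil's side effects "with nausea, headache, dizziness, and vomiting being the most common". No rate is given for standard care, for hypotension or for airway events.

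**Time windows.** Section IV, Secondary Outcome Definitions, defines two safety outcomes. For the symptoms: "The incidence of nausea, vomiting, headache, and/or dizziness requiring treatment will be recorded for initial 30 minutes, when feasible". For hypoxia, hypotension and advanced airway management, the definition runs longer and ends "placement of an endotracheal tube, supraglottic airway or bag mask ventilation) until ED discharge (up to 120 minutes".

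**Wording of the endpoint.** The Secondary Outcomes paragraph of Section IV lists the "incidence of nausea/vomiting/headache/dizziness requiring treatment" without a window. Hypothesis #2 in Section I has neither the window nor the limit to treated symptoms: "There will be no difference in the rate of adverse events of nausea/vomiting, headache, dizziness, hypoxia, hypotension and need for advanced airway". The Aim #2 text in Section VI likewise has neither.

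**The concern.** The main concern is the adjusted analysis of the individual events. A logistic model estimates the treatment effect as a difference in log-odds. If one arm has no events, the likelihood keeps rising as that arm's fitted probability goes to zero, so the estimate runs to infinity and its standard error is meaningless. If neither arm has an event, there is no treatment effect to estimate. With 75 patients per arm and a component near the rate quoted in Section II, such tables are the likely result. The plan would then need a method chosen after the data are seen, in an open-label trial, for components that Section IV places in the principal safety outcome.

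The lesser concern is what the pooled Aim #2 composite measures. It joins treated symptoms from the first 30 minutes with hypoxia, hypotension and airway events from up to 120 minutes. It would count hypoxia at 60 minutes but not vomiting treated at 60 minutes. The analysis text does not say that each event keeps its own window, nor that only treated symptoms count.

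**Working it through.** **Inputs.** 75 patients per arm (Section VI, Sample Size) and site as the stratification factor (Section VI, Random Assignment). The plan states no rate or power for Aim #2, so there is no figure of its own to reproduce. The event rates below are assumptions, chosen around the rate below 1% in Section II.

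**Step 1: chance of an empty arm.** With true rate p in both arms, one arm is empty with probability z = (1 - p)^75. Exactly one arm is empty with probability 2z(1 - z), both with z², and at least one with 1 - (1 - z)².

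At p = 1%: z = 0.99^75 = 0.471. Exactly one empty: 2 × 0.471 × 0.529 = 0.498. Both empty: 0.471² = 0.222. At least one: 0.720.

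| Assumed rate, both arms | Exactly one arm empty | Both empty | At least one empty |
|---|---|---|---|
| 0.5% | 43% | 47% | 90% |
| 1% | 50% | 22% | 72% |
| 2% | 34% | 5% | 39% |
| 3% | 18% | 1% | 19% |
| 5% | 4% | under 0.1% | 4% |
| 10% | under 0.1% | about 0 | under 0.1% |

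With unequal rates of 1% and 5%, z is 0.471 and 0.021, and the chance of at least one empty arm is 1 - 0.529 × 0.979 = 48%.

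**Step 2: what the stated model does.** Take 0/75 against 3/75 with two sites assumed. The ordinary treatment log-odds is -8.4 after 10 iterations, -18.4 after 20 and -28.4 after 30. Its standard error goes from 23 to about 3,400 to about 500,000. There is no finite maximum.

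**Step 3: what the alternative does.** On the same table, Firth logistic regression adjusted for site gives an odds ratio of 0.14. The profile 95% interval runs from 0.001 to between 1.45 and 1.47, depending on how patients and events are split between sites. The interval is wide, but it can be reported. When an arm has no events, its exact 95% upper limit is 1 - 0.025^(1/75) = 4.8%.

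**Step 4: does the chi-square test also need replacing?** It can be computed with one empty arm: for 0/75 against 3/75 the statistic is 3² × 150 / (3 × 147) = 3.06, below 3.84. By full enumeration at a nominal 0.05, its actual size is 0.0065 at 1%, 0.029 at 2%, 0.049 at 5% and at most 0.053 at the rates checked (1% to 10%). Against assumed rates of 1% and 8%, its power is 58%, compared with 36% for Fisher's exact test. Replacing it would cost power to detect a safety difference and gain little.

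**Step 5: the composite, definition by definition.**

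| | Four symptoms | Hypoxia, hypotension, airway |
|---|---|---|
| Window in Section IV definitions | first 30 minutes | to ED discharge, at most 120 minutes |
| Limited to treated events | yes | no such limit in the definition |
| Window in Section VI, Aim #2 | none given | none given |
| Limit to treated events in Section VI, Aim #2 | absent | not applicable |

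Scoring each event by its own Section IV window is possible, but it gives a single proportion covering two risk periods. The documents give neither symptom rates nor timing, so the number of later symptoms cannot be derived.

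**The case against.** **On the model.** The fault touches only the adjusted estimate for individual rare components. The chi-square test comes first in the plan and survives. A failed fit is visible to any analyst and would not mislead silently. The 72% and 90% figures need the low rate in both arms. Section II gives it only for respiratory depression and hypoxia with sufentanil, and the source it cites is a study after abdominal surgery. This trial enrols trauma activations and allows earlier narcotics. All of this stands, which is why the range is shown: at 3% the chance of an empty arm is 19%, and at 5% it is 4%. The principal safety outcome combines three components, so it has at least as many patients with an event as any one of them. What remains is that the plan requires this model for every event and names nothing to use when it fails.

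**On the windows.** Thirty minutes is a defensible choice. It matches the primary outcome, the cognitive screen and the professional's global assessment, and it leaves out symptoms that follow later rescue narcotics. Section X separately documents related adverse events through the end of participation, though as safety reporting and not as the Aim #2 endpoint. Leaving operational detail out of the aims is normal.

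A reader might infer that the mixed windows bias the arm comparison. The documents do not support that: both arms share the same windows, and the 30-minute symptom result is valid as a 30-minute result. A reader might also infer that symptoms must be recorded to ED discharge. That is a trade-off. The trial is open label, treating physicians know the arm, and eligibility requires only an estimated stay above 30 minutes. Both the treatment of symptoms and the length of follow-up could therefore differ by arm.

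**Conclusion.** The point holds as a minor one. For a component at 1% in both arms, the stated adjusted analysis has a 72% chance of giving no usable treatment estimate: 50% with no finite estimate and 22% with nothing to estimate. This rests on equal assumed rates and 75 patients per arm. The chance falls quickly as the rate rises, and it does not arise for common symptoms (under 0.1% at 10%). It would be too strong to say that the Aim #2 analysis as a whole fails or that its chi-square test is unsound.

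The composite covers two risk periods, and Section VI does not say how to score it. Neither a bias nor a size is shown. The missing limit to treated symptoms is, taken alone, missing detail that Section IV supplies.

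**What to change.** **Model, Section VI, Aim #2.** For sparse components, replace ordinary logistic regression with Firth penalised logistic regression adjusted for site, and report counts with an exact confidence interval for the risk difference. If neither arm has an event, report counts and exact intervals only. Keep the chi-square test. Define sparse in advance, for example as fewer than ten events over both arms together or none in one arm; ten events in total is where the expected count per arm reaches 10/2 = 5. The cost is a sentence or two in the analysis plan. The downside is wide intervals, which reflect how little information the data hold.

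**Composite, Section VI, Aim #2.** Either report the two Section IV safety outcomes separately, each with its own window, or pool all events at 0-30 minutes. State that symptoms count only if they required treatment. This costs one sentence and no new data collection, provided that event times are recorded if the 0-30 minute option is chosen. Pooling at 0-30 minutes leaves later hypoxia, hypotension and airway events out of the composite, so the longer-window outcome should still be reported beside it.

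**Optional.** Symptoms could also be recorded to ED discharge as a supplementary result. That needs a form and protocol change, and the possible differences by arm in follow-up and symptom treatment would limit its interpretation.

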#### **Richmond Agitation-Sedation Scale (RASS) score at 30-minute intervals:**

A RASS score at approximate 30-minute intervals until discharge from the ED (up to 120 minutes) or rescue narcotic administration, will be obtained when feasible. (-5 to 4+; 10-point scale).

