# Protocol Synopsis

Protocol Title:	DSUVIA Early Evaluation of Pain (DEEP) Trial				
Protocol Number:	STUDY21100180				
NCT Number:	NCT05288348				
Version # and Date:	Version 3 1/12/2023				
Investigational Drug:	DSUVIA as compared to standard care pain treatment				
Trial Sites:	
 
Clinical Coordinating Center
 
University of Pittsburgh, University of Pittsburgh Medical Center, Co-PI [name], Co-PI [name]
 
Additional Sites:
 
TBD
 
				
Funding Agency	Department of Defense				
Study Aims:	
 
Objectives for the study aims: 
 
(1) To conduct a prospective, randomized, interventional trial to examine effectiveness, safety, and acceptability of DSUVIA compared to standard care pain treatment in an emergency department (ED) setting in patients following traumatic injury with moderate to severe pain.
 
(2) To analyze pain treatment effectiveness outcomes including: 
 
a. Verbally administered Numeric Rating Scale (VNRS) for clinical pain measurement (0-100) 30 minutes after pain medication administration
 
b. Adverse effects and events related to pain medication(s) including nausea/vomiting, headache, dizziness, hypoxia, hypotension, and need for advanced airway
 
c. Verbally administered Numeric Rating Scale (VNRS) for clinical pain measurement (0-100) at 30-minute intervals until discharge from the ED (up to 120 minutes) or rescue narcotic administration
 
d. Patient Global Assessment (PGA) of Pain Control at 30-minute intervals until discharge from the ED (up to 120 minutes) or rescue narcotic administration
 
e. Richmond Agitation-Sedation Scale score at 30-minute intervals until discharge from the ED (up to 120 minutes) or rescue narcotic administration
 
f. Time-weighted summed pain intensity difference (SPID) at 30-minute intervals until discharge from the ED (up to 120 minutes) or rescue narcotic administration
 
 
 

				

	
 
g. Number of rescue doses of narcotic at 30 minutes and during ED stay (up to 120 minutes)
 
h. Time to reduction of NRS pain score of 10 points
 
i. Cognitive function assessment with the Six Item Screener (SIS) at 30 minutes
 
j. Healthcare Professional Global Assessment (HPGA) of the Method of Pain Control at 30 minutes
 
k. Acceptability to health care providers survey
 
			
Study Design:	Prospective, randomized, interventional trial			

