#### **Time-weighted Summed Pain Intensity Difference (SPID) at 30-minute intervals:**

Time-weighted SPID measurements will be calculated at approximate 30-minute intervals until discharge from the ED (up to 120 minutes) or rescue narcotic administration, will be determined when feasible. Essentially, the SPID represents serial assessments of pain intensity over time, weighted by time differences. SPID will be calculated using values from a 101-point continuous pain intensity scale (0 = no pain to 100= worst pain imaginable). The Pain Intensity Difference (PID) (e.g., raw differences in pain intensity) is calculated by subtracting the pain intensity at each time point from the pain intensity at time 0. The SPID is then calculated by multiplying the PID score at each post dose time point by the duration (in hours) since the preceding time point and then summing the values over the relevant time period. If patients did not complete the full 120 minutes, the last pain observation was carried forward.

#### Number of rescue doses of narcotic at 30 minutes and until ED discharge (up to 120

**minutes):** The number of doses of standard care pain treatment given within 30 minutes following randomly assigned intervention and total until ED discharge (up to 120 minutes), when feasible.

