## IX. Human Subjects

We anticipate that this study will be conducted utilizing a written informed consent while the patient resides in the ED.

Study Risks and Benefits: Risks associated with pain management include allergic reaction, hypoxia requiring oxygen, (SPO2 < 90%), hypotension (SBP < 90 mmHg), or need for advanced airway management (placement of an endotracheal tube or supraglottic airway) following medication administration.

Regardless of treatment arm, we anticipate that enrolled subjects will benefit from increased monitoring of primary and secondary outcomes, specifically, a focus on adequate pain control and pain management complications including respiratory compromise, hypotension, decreased sensorium, and need for advanced airway control.

Institutional Review Board: A central IRB at the University of Pittsburgh will be utilized for the regulatory needs of studies. All current LITES Network sites have IRBs which have experience and engagement with central IRB procedures.

Training and Participating Site Coordination: As the clinical coordinating center for the trial, the University of Pittsburgh (LITES) at the University of Pittsburgh will be collaboratively responsible for all research coordinator training, provider training. Research coordinators, providers and associated staff will be trained during the months prior to the trial start date regarding the scientific basis for the study, specific inclusion and exclusion criteria, study procedures and SOPs. Training verification and retraining will occur if new staff is hired at individual participating sites.

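### Sedation scoring (RASS) stops at rescue narcotic, so sedation after an added opioid is not systematically scored and the arm comparison depends on who is rescued and when

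*Combined protocol and SAP*

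**What the plan says.** Three places set the RASS schedule, and they agree. The RASS definition in section IV asks for "A RASS score at approximate 30-minute intervals until discharge from the ED (up to 120 minutes) or rescue narcotic administration". The Secondary Outcomes paragraph of section IV puts RASS in one list with VNRS, PGA and SPID under "serial (30 minute intervals until ED discharge, up to 120 minutes or rescue narcotic administration) measurements". The synopsis (study aims, item e) has "Richmond Agitation-Sedation Scale score at 30-minute intervals until discharge from the ED (up to 120 minutes) or rescue narcotic administration". No section schedules a RASS score after rescue.

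Rescue itself is described by how it is counted: "The number of doses of standard care pain treatment given within 30 minutes following randomly assigned intervention and total until ED discharge" (rescue-dose definition, section IV).

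Other measures have other windows. The principal safety outcome (hypoxia, hypotension, advanced airway management) is followed "until ED discharge (up to 120 minutes), when feasible", with no stop at rescue. The Six Item Screener (SIS) is given once, at 30 minutes. Section IX expects enrolled subjects to benefit from closer attention to "pain management complications including respiratory compromise, hypotension, decreased sensorium, and need for advanced airway control".

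RASS is analysed under Aim 3, treatment effectiveness, by a Wilcoxon test and then a nonparametric regression adjusted for site and unbalanced baseline characteristics. Section VI also states: "All analyses will be carried out based on the intention-to-treat principle".

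**The concern.** Stopping pain scores at rescue has a clear rationale: once another analgesic is on board, the score no longer describes the assigned drug alone. That reasoning does not carry over well to sedation, where an added opioid increases the exposure of interest. The rule therefore ends measurement just when the question becomes more relevant.

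The second difficulty is comparability. Rescue happens after randomization and may depend on the arm. DSUVIA is a single dose. In the standard care arm, a repeat dose of the usual narcotic appears to meet the same rescue definition and would also end RASS. If rescue differs between arms in frequency or timing, each arm's RASS data come from a differently selected set of patients and times. Section II lists little effect on mental status among the features of an ideal agent, so sedation bears on the trial's rationale. Scores that are not taken cannot be recovered later.

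**Working it through.** No figure in the plan rests on this rule, so there is none to reproduce. The check compares the windows, counts the scores lost, and then shows with assumed rates what could be hidden.

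**1. Windows, side by side (section IV)**

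| Measure | Scheduled | Stops at rescue? |
|---|---|---|
| VNRS, PGA, SPID | about every 30 min, 120 min at most | yes |
| RASS | about every 30 min, 120 min at most | yes |
| SIS | once, at 30 min | no stop stated |
| Hypoxia, hypotension, airway | through the ED stay, 120 min at most | no |
| Nausea, vomiting, headache, dizziness needing treatment | first 30 min | no stop stated |

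A patient rescued after 30 minutes has no planned sedation or cognition score from then on. A patient rescued earlier still has the 30-minute SIS, which gives an indirect reading of sleepiness.

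**2. RASS scores lost, for a patient who stays the full 120 minutes (scores at 30, 60, 90 and 120)**

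- Rescue before 30 min: 4 of 4 lost, so no post-dose RASS at all.
- Rescue between 30 and 60 min: 3 lost.
- Rescue between 60 and 90 min: 2 lost.
- Rescue between 90 and 120 min: 1 lost.

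A shorter ED stay loses fewer.

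**3. Patients affected.** The documents give no rescue rate. With 75 per arm (Sample Size, section VI) and an assumed 10% to 50% rescued:

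- 75 × 0.10 = 7.5, about 8 patients per arm
- 75 × 0.50 = 37.5, about 38 patients per arm

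**4. What could be hidden.** All rates here are assumed. Suppose over-sedation occurs in 2% of unrescued patients and in 10% to 20% of rescued patients, arising after rescue. Let 20% be rescued in arm A and 40% in arm B.

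- Rescued rate 10%: A = 0.8 × 2% + 0.2 × 10% = 3.6%; B = 0.6 × 2% + 0.4 × 10% = 5.2%; difference 1.6 points.
- Rescued rate 20%: A = 0.8 × 2% + 0.2 × 20% = 5.6%; B = 0.6 × 2% + 0.4 × 20% = 9.2%; difference 3.6 points.

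RASS confined to time without rescue would show about 2% in both arms. The hidden difference is 75 × 1.6% = 1.2 to 75 × 3.6% = 2.7 patients per arm: few in number, but all of the contrast in this example.

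**5. Direction.** In step 4 the arm with more rescue looks safer than it is. The opposite is also possible. If rescued patients are those still in pain and more alert, removing them leaves a more sedated remainder, and the arm with more rescue looks worse at 60 to 120 minutes. Data collected under the current rule could not tell the two apart.

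**The case against.** The strongest reply is that the rule is deliberate and consistent. RASS sits in Aim 3 with the pain scores and shares their window, which describes the assigned drug before rescue confounds it. The plan has no single safety window for RASS to break, since nausea, vomiting, headache and dizziness are recorded for 30 minutes only. The primary outcome and the principal safety outcome are untouched. All of this stands, and it is why the pre-rescue view deserves to be kept. It does not justify leaving post-rescue scores untaken, because the pre-rescue view can always be derived from fuller data and the reverse is impossible.

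Several stronger readings are tempting, and the documents do not support them.

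- **A known two-hour overlap of sedating drugs.** Section II reports "pain reduction seen in less than 15 minutes and persisting for 2 hours". That figure is for analgesia in a cited cohort and gives no duration of sedation.
- **RASS would describe only single-opioid patients.** Section III allows narcotics before randomization in both arms, so an unrescued patient may already have received more than one.
- **Missing-at-random imputation would fill the post-rescue scores.** The Missing data paragraph does not say that scores after the defined end of measurement count as missing.
- **Over-sedation would go unnoticed.** Section X has related adverse events assessed from enrollment to the end of participation, and respiratory consequences fall under the principal safety outcome. What is lost is a scheduled score.
- **The intention-to-treat statement already requires scoring after rescue.** Section VI uses the term to mean analysis by randomized group (see its paragraphs on ineligible subjects and non-adherence).
- **A definite share of sedation episodes is missed.** Any such percentage rests wholly on assumed rates.

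**Conclusion.** The concern holds as a defect in measurement and comparison for one secondary outcome. Followed as written, the plan leaves sedation after an added opioid without systematic scores and makes the RASS comparison conditional on a post-randomization event. That part follows directly from the schedule. That rescue will differ between arms is an inference: it is plausible given one fixed dose against repeatable standard care, but it is not stated. The direction of any bias is open and its size unknown; the rates used above are illustrations. The change is worth making because it is cheap and the lost scores are irrecoverable, not because the trial's main conclusions are at risk.

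**What to change.** For RASS only, remove the clause that ends scoring at rescue, in the synopsis (item e), the Secondary Outcomes paragraph and the RASS definition. In the Secondary Outcomes paragraph RASS must be taken out of the shared list, so that VNRS, PGA and SPID keep their present window. Score RASS about every 30 minutes while the patient is in the ED, to a maximum of 120 minutes, whether or not rescue is given, and record the time of rescue. Under Aim 3, make the comparison of all RASS scores by randomized group the sedation result, with scores up to rescue as a supporting analysis.

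The cost is an edit in three places, a line in Aim 3, and up to four extra bedside scores in a patient rescued before 30 minutes (up to three if rescued later). These patients are already followed for hypoxia, hypotension and airway events. Post-rescue scores will reflect assigned treatment plus rescue; the recorded rescue time lets the analyst separate the two periods. No treatment or rescue rule changes.
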